4.4. Study Visit Flow Diagram

* Day 0 (Visit 2) should occur within 7 days of screening.

5.0 DRUG/DEVICE/BIOLOGIC AGENT INFORMATION

5.1. Influenza Virus Vaccine

The influenza virus vaccine can be of any licensed brand, preferably Fluzone.

5.2. Vitamin A and D3 Nutritional Supplements, Oral

Vitamin A palmitate 20,000 International Units and Vitamin D3 2,000 International Units liquid formulations will be compounded with gelatin base, tangerine oil, polysorbate 20F, citric acid anhydrous USP, and steviol glycosides 95% into a chewable gummy. The gummies will be compounded for participants by Regal PharmaLab (a local compounding pharmacy) following U.S. Pharmacopeial Convention (USP) 795 good compounding practices for pharmaceutical compounding of nonsterile preparations.

The expiration date will be listed on the product label for storage at controlled room temperature. Individual doses will be dispensed with participant name, medical record number, dosing instructions, and date. St. Jude Children's Research Hospital Pharmacy will dispense the gummies and keep accountability records as per randomized assignment.

Certificates of Analysis (CoA) are available for the Vitamin A palmitate liquid, Vitamin D3 liquid, gelatin base, tangerine oil, polysorbate 20 NF, citric acid anhydrous USP, and steviol glycosides 95%. As vitamin supplements, these products are not FDA approved for prevention, diagnosis or treatment of disease.

5.3. Matched Placebo

Placebo gummies will be compounded for participants by Regal PharmaLab (local compounding pharmacy) following U.S. Pharmacopeial Convention (USP) 795 good compounding practices for pharmaceutical compounding of nonsterile preparations. The placebo gummies will be formulated with gelatin base, tangerine oil, polysorbate 20 NF, citric acid anhydrous USP, and steviol glycosides 95% and will match the Vitamin A and D3 gummies in shape, taste, texture, and appearance.

The expiration date will be listed on the product label for storage at controlled room temperature. Individual doses will be dispensed with participant name, medical record number, dosing instructions, and date. St. Jude Children's Research Hospital Pharmacy will dispense the gummies and keep accountability records as per randomized assignment.

Certificates of Analysis (CoA) are available for the gelatin base, tangerine oil, polysorbate 20 NF, citric acid anhydrous USP, and steviol glycosides 95%.

6.0 REQUIRED EVALUATIONS, TESTS, AND OBSERVATIONS

A summary of the evaluations described below and their schedule for completion can be found in Appendix I. Protocol related procedures, evaluations, and labs not performed as scheduled due to malfunctioning equipment, participant non-compliance, participant need or preference (e.g., vacation), participant condition or due to falling on a weekend or holiday will be noted in the participant study record but not be reported as deviations. Adverse events related to commercially available influenza virus vaccine will also not be collected as part of this study.

6.1. Screening Visit

At the screening visit, after informed consent is obtained the following will be completed:

Medical History to include:

- History of a severe allergy to eggs or to any inactive ingredient in the influenza virus vaccine
- History of a life-threatening reaction to influenza vaccinations
- History of Guillain-Barre syndrome
- Currently wheezing or history of wheezing if under 5 years old
- History of immunodeficiency
- History of heart, kidney, or lung problems
- History of diabetes
- Currently taking Tamiflu, Relenza, Amantadine, and/or Rimantadine
- Currently taking daily vitamin or multivitamin

Laboratory Evaluations

- Serum for vitamin studies
- Serum for immunologic studies

Questionnaires

- Socio-demographic questionnaire

Once screening criteria is confirmed and vitamin A retinol protein levels have been resulted, the participant will be randomized.

6.2. Day 0 (Vaccine dose #1) Visit

For the purposes of this study, Study Day 0 is defined for each participant as the day that the first vaccine (Influenza virus vaccine) is administered.

Day 0 must be completed within 10 days of the screening assessment. If greater than 10 days passes, the participant must repeat the screening visit to confirm eligibility.

All Screening and Entry visit data must be collected prior to the receipt of vaccination and vitamin (A and D) dose #1. Vitamin or placebo chewable

gummy must be administered prior to influenza virus vaccine dose administration.

The following will be collected as a part of the Entry Visit:

- Chewable gummy (vitamin supplements or placebo depending on randomization) dose administration
- Administration of influenza virus vaccine Dose #1 for intervention and control group and observation in clinic 30 minutes post-vaccine administration
- Dispense food diary to control and intervention participants.
- Serum for vitamin studies
- Serum for immunologic studies

6.3. Day 28 (Vaccine dose #2) Visit

The following will be completed:

- Interim medical history and medication use
- Laboratory evaluations
 - Serum for vitamin studies
 - Serum for immunologic studies
- Collection of food diary from participants
- Administration of influenza virus Vaccine Dose #2 to Intervention and Control group participants
- Administration of chewable gummy dose #2
- Dispense food diary to control and intervention participants.

6.4. Day 56 Follow-Up Visit

The following will be completed:

- Interim Medical History and medication use
- Collect food diary from participants
- Laboratory evaluations:
 - Serum for vitamin studies
 - Serum for immunological studies
- At day 56, participants enrolled after approval of Revision 1.1, will be given the option to complete the Block food frequency questionnaire (FFQ). This questionnaire includes about 90 questions and asks about a child's "usual eating habits in the past 6 months." It takes a caregiver or interviewer approximately 30 minutes to complete. The food list was

developed from NHANES III dietary recall data. The nutrient database was developed from the USDA Nutrient Database for Standard Reference. Individual portion size is asked for beverages but not other foods. Dietary information obtained from this questionnaire is for exploratory purposes only.

6.5. Special Instructions and Definitions of Evaluations

Study Visit Windows

Day 0 (Vaccine dose #1) visit must occur within 10 days of screening.

Day 28 (Vaccine dose #2) visit must be performed within +3 days of the protocol specified date

Day 56 (follow-up)visit must be performed within +/- 7 days of the scheduled protocol visit date.

Vaccination

Influenza virus vaccines will be administered per manufacturer's recommendations by trained study or clinic staff.

Participant caregivers will be informed to contact their child's PCP should any influenza virus vaccine related reactions occur over the course of the study.

Vitamins A and D3

Chewable vitamin supplements or placebo gummies will be administered orally to participants prior to receiving the influenza virus vaccine on Day 0 and Day 28 by study staff. The gummy will be administered and documented in the participants research record prior to the influenza virus vaccine vaccination..

Laboratory Evaluations

Immune responses (inclusive of IgM, IgG, IgA, and cytokines) will be measured in blood serum collections at Screening, Day 28, and Day 56. ELISAs and functional assays (neutralization or HAI assays) will examine virus-specific and total antibodies. Serum vitamins A and D will be tested by HPLC and/or tests standardized against HPLC, and with a surrogate retinol binding protein assay.

7.0 EVALUATION CRITERIA

7.1. Toxicity Evaluation Criteria

All adverse events will be graded by the Pediatric Toxicity Grading Tables from the Division of Microbiology and Infectious Diseases (DMID). See Appendix III for details.

7.2. Acceptable Percentage of Missed Doses for Research and Standard of Care Drugs

All eligible participants who receive at least one dose of vaccine will be included in the data analyses.

8.0 CRITERIA FOR REMOVAL FROM PROTOCOL THERAPY AND OFF-STUDY CRITERIA

8.1. Off-study criteria

Completion of study (completion of the final follow-up visit)

Development of Influenza infection and/or receipt of anti-influenza medications during the study period

Death

Lost to follow-up

Request of the Participant/Parent

Discretion of the Study PI, such as the following

- The researcher decides that continuing in the study would be harmful
- A treatment is needed that is not allowed on this study
- The participant misses so many appointments that the data cannot be used in the study
- New information is learned that a better treatment is available, or that the study is not in the participant's best interest
- Study evaluations are complete

9.0 SAFETY AND ADVERSE EVENT REPORTING REQUIREMENTS

9.1. Reporting Adverse Experiences and Deaths to St. Jude IRB

Only “unanticipated problems involving risks to participants or others” referred to hereafter as “unanticipated problems” are required to be reported to the St. Jude IRB promptly, but in no event later than 10 working days after the investigator first learns of the unanticipated problem. Regardless of whether the event is internal or external (for example, an IND safety report by the sponsor pursuant to 21 CFR 312.32), only adverse events that constitute unanticipated problems are reportable to the St. Jude IRB. As further described in the definition of unanticipated problem, this includes any event that in the PI’s opinion was:

- Unexpected (in terms of nature, severity, or frequency) given (1) the research procedures that are described in the protocol-related documents, such as the IRB-approved research protocol and informed consent document, as well as other relevant information available about the research; (2) the observed rate of occurrence (compared to a credible baseline for comparison); and (3) the characteristics of the subject population being studied; and
- Related or possibly related to participation in the research; and
- Suggests that the research places subjects or others at a greater risk of harm (including physical, psychological, economic, or social harm) than was previously known or recognized. An unanticipated problem involving risk to subjects or others may exist even when actual harm does not occur to any participant.

Unrelated, expected deaths do not require reporting to the IRB. Though death is “serious”, the event must meet the other two requirements of “related or possibly related” and “unexpected/unanticipated” to be considered reportable.

Deaths meeting reporting requirements are to be reported immediately to the St. Jude IRB, but in no event later than 48 hours after the investigator first learns of the death.

The following definitions apply with respect to reporting adverse experiences:

Serious Adverse Event:

Any adverse event temporally associated with the subject’s participation in research that meets any of the following criteria:

- results in death;
- is life-threatening (places the subject at immediate risk of death from the event as it occurred);
- requires inpatient hospitalization or prolongation of existing hospitalization;
- results in a persistent or significant disability/incapacity;
- results in a congenital anomaly/birth defect; or
- any other adverse event that, based upon appropriate medical judgment, may jeopardize the subject's health and may require medical or surgical intervention to prevent one of the other outcomes listed in this definition (examples of such events include: any substantial disruption of the ability to conduct normal life functions, allergic bronchospasm requiring intensive treatment in the emergency room or at home, blood dyscrasias or convulsions that do not result in inpatient hospitalization, or the development of drug dependency or drug abuse), a congenital anomaly/birth defect, secondary or concurrent cancer, medication overdose, or is any medical event which requires treatment to prevent any of the medical outcomes previously listed.

Unexpected Adverse Event:

- Any adverse event for which the specificity or severity is not consistent with the protocol-related documents, including the applicable investigator brochure, IRB approved consent form, Investigational New Drug (IND) or Investigational Device Exemption (IDE) application, or other relevant sources of information, such as product labeling and package inserts; or if it does appear in such documents, an event in which the specificity, severity or duration is not consistent with the risk information included therein; or
- The observed rate of occurrence is a clinically significant increase in the expected rate (based on a credible baseline rate for comparison); or
- The occurrence is not consistent with the expected natural progression of any underlying disease, disorder, or condition of the subject(s) experiencing the adverse event and the subject's predisposing risk factor profile for the adverse event.

Internal Events:

Events experienced by a research participant enrolled at a site under the jurisdiction of St. Jude IRB for either multicenter or single-center research projects.

Unanticipated Problem Involving Risks to Subjects or Others:

An unanticipated problem involving risks to subjects or others is an event which was not expected to occur and which increases the degree of risk posed to research participants. Such events, in general, meet all of the following criteria:

- unexpected;
- related or possibly related to participation in the research; and
- suggests that the research places subjects or others at a greater risk of harm (including physical, psychological, economic, or social harm) than was previously known or recognized. An unanticipated problem involving risk to subjects or others may exist even when actual harm does not occur to any participant.

Consistent with FDA and OHRP guidance on reporting unanticipated problems and adverse events to IRBs, the St. Jude IRB does not require the submission of external events, for example IND safety reports, nor is a summary of such events/reports required; however, if an event giving rise to an IND safety or other external event report constitutes an “unanticipated problem involving risks to subjects or others” it must be reported in accordance with this policy. In general, to be reportable external events need to have implications for the conduct of the study (for example, requiring a significant and usually safety-related change in the protocol and/or informed consent form).

Although some adverse events will qualify as unanticipated problems involving risks to subjects or others, some will not; and there may be other unanticipated problems that go beyond the definitions of serious and/or unexpected adverse events. Examples of unanticipated problems involving risks to subjects or others include:

- Improperly staging a participant’s tumor resulting in the participant being assigned to an incorrect arm of the research study;
- The theft of a research computer containing confidential subject information (breach of confidentiality); and
- The contamination of a study drug. Unanticipated problems generally will warrant consideration of substantive changes in the research protocol or informed consent process/document or other corrective actions in order to protect the safety, welfare, or rights of subjects or others.

9.2. Recording Adverse Events and Serious Adverse Events

Adverse events associated with the influenza virus vaccine will not be recorded for this study. Other adverse events will be graded using the Division of Microbiology and Infectious Diseases (DMID) Pediatric Toxicity Tables (Appendix III). All grades of these events will be recorded.

Adverse events will be collected from enrollment through the participant's last visit. Any AE that has not had a stop date recorded by the participant's last visit will continue to be followed-up until an outcome or resolution has occurred. Study participants will be instructed to notify study personnel at any time during the study if they are hospitalized or have any unusual, alarming or unexpected events.

Adverse events will be assessed by the investigator for severity, relationship to the study product, possible etiologies and whether the event meets criteria as a serious adverse event.

The following guidelines will be used by investigators to assess the relationship of an AE to study product administration:

- Definite: Unquestionable relationship. The event was directly attributable to the study product.
- Probable: Relationship is likely. It is likely that the study product caused the event.
- Possible: Relationship may exist. There is at least a reasonable possibility that the event was caused by the study product, although the likelihood is low.
- Unlikely: Relationship is not likely. Although it is unlikely that the study product caused this event, causality cannot be entirely ruled out.
- Unrelated: No relationship. The study product did not cause the event.

Factors considered in assessing the relationship of an AE to study product include:

- the temporal relationship of the event to the administration of study product;
- whether an alternative etiology has been identified; and
- biological plausibility.

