Participants will be randomized to receive either influenza virus vaccine plus vitamins A and D supplements (n=40) or influenza virus vaccine plus matched placebo. Gummies for the intervention and control arm (placebo) will be provided in the same container by an unblinded pharmacist to maintain blinding. For the purposes of this study, Study Day 0 is defined for each participant as the day that the first influenza vaccine dose is administered. All participants will receive 2 doses of influenza virus vaccine at least 28 days apart.

Children will have the first influenza virus vaccine dose (dose 1) administered on day 0 of the trial, and the second dose (dose 2) administered 28 days later.

Vaccines will be administered by a technique consistent with the manufacturer's specification.

Participants will be observed for 30 minutes following vaccination. Participants will be given a food diary card to record their diet between the Day 0 and Day 56 study visits.

Blood serum samples will be collected from participants at Screening and prior to receiving the influenza virus vaccine on Day 28 as well as during their Day 56 follow-up visit.

Chewable Vitamin or Placebo Administration

Chewable Vitamin A & D3 or Placebo Gummy

The chewable gummy contains either Vitamin A (20,000 International Units) and Vitamin D3 (2,000 International Units) or matched placebo, which should be fully chewed under supervision of study staff with documentation in the participants research record and eMAR (electronic medical administration record). The chewable gummy should be administered prior to receiving influenza virus vaccine vaccination.

If participants have difficulty chewing the gummy, another option is to cut the chewable vitamin in half along score line for easier administration.

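### Vaccine-attributed adverse events are left unrecorded, so they cannot be compared systematically between the vitamin and placebo arms: a modest, cheaply avoided loss of descriptive safety information

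*Combined protocol and SAP*

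**What the plan says.** Two sections of the protocol set the rule. Section 9.2: "Adverse events associated with the influenza virus vaccine will not be recorded for this study". Section 6.0: "Adverse events related to commercially available influenza virus vaccine will also not be collected as part of this study". They agree, so the rule is deliberate. Under 9.2, other adverse events are recorded at all grades from enrollment to the last visit. Section 7.1, by contrast, applies the DMID paediatric tables to all adverse events without carving out vaccine reactions.

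On timing, section 4.1 says "The chewable gummy should be administered prior to receiving influenza virus vaccine vaccination", and section 6.5 has the gummy given "prior to receiving the influenza virus vaccine on Day 0 and Day 28 by study staff".

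On attribution, section 9.2 has the investigator assess "relationship to the study product, possible etiologies and whether the event meets criteria as a serious adverse event". Its Possible level reads "There is at least a reasonable possibility that the event was caused by the study product, although the likelihood is low". Among the listed factors is whether another cause has been found.

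On reactions at home, section 6.5 says "Participant caregivers will be informed to contact their child's PCP should any influenza virus vaccine related reactions occur over the course of the study". Section 9.2 also has participants told to "notify study personnel at any time during the study if they are hospitalized or have any unusual, alarming or unexpected events". The only participant diary in Appendix I is for food.

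**The concern.** Both arms receive the vaccine minutes after the randomised product, so any acute event follows both. Under the rule, a causal judgement comes first and decides whether the event enters the record at all. The vaccine is always available as another cause. The filter can therefore remove more than true vaccine reactions: an event due to the gummy, or to the two products together, is lost if it is labelled a vaccine reaction.

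Section 9.2 partly deals with this through its Possible level and its request for possible etiologies. It does not say that an event possibly due to either product is kept, nor that a serious event attributed to the vaccine is recorded.

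At stake is descriptive tolerability information from a blinded, placebo-controlled pilot in children aged 2 to 8, intended to inform larger studies of the same combination. The concurrent placebo arm is the natural comparator for reactions after vaccine plus gummy, and its vaccine-attributed events go unrecorded too.

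**Working it through.** The plan states no adverse event rate, interval or power, so there is no figure of its own to reproduce. The check has three parts.

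**1. Sections side by side**

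| Section | What it provides | Does it give a by-arm record of vaccine-attributed events? |
|---|---|---|
| 6.0 and 9.2 | Neither collected nor recorded | No |
| 7.1 | Grading of all adverse events | No; an unrecorded event cannot be graded |
| 4.1, 6.2, Appendix I | 30-minute observation after vaccination | Immediate period only; no recording exception stated |
| 6.3, 6.4, Appendix I | Medical history at Days 28 and 56 and at early discontinuation | Partial and recalled |
| 4.3 | Medications through Day 56 | Indirect |
| 9.2 | Notification of hospitalisation or unusual events | Partial |
| 9.1 | IRB reporting of unanticipated problems | Only that subset |
| 10.2 | Monitor review of serious event reporting for selected participants; IRB review of serious event reports | Oversight, not a by-arm record |
| 11.4 | No adverse event summary of any kind | No |

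Nothing restores systematic recording.

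**2. What the filter does to a difference**

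Suppose a share s of acute events is labelled vaccine-related, equally in both arms because attribution is blinded. Then recorded difference = (1 − s) × true difference. The rates here are assumptions, since the documents give none: 35% versus 20%, a true difference of 15 points.

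- s = 0.25: 0.75 × 15 = 11.25 points
- s = 0.5: 0.5 × 15 = 7.5 points
- s = 1: 0 points

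Under this assumption the filter dilutes a difference and does not favour an arm.

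**3. What recording would give**

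Inputs: 40 per arm (section 11.2); or 50 per arm, from about 100 enrolled equally into two groups (section 4.1), assuming all are dosed. The 38 per arm in 11.2 (40 × 0.95) is the number expected to give primary-endpoint data, not a safety denominator; sections 3.5 and 7.2 keep every eligible child given at least one vaccine dose in the analyses.

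Upper limit for 0 events in n (Clopper-Pearson, two-sided 95%): 1 − 0.025^(1/n).

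- n = 40: 1 − 0.025^(1/40) = 0.088, or 8.8%
- n = 50: 1 − 0.025^(1/50) = 0.071, or 7.1%

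Widest 95% interval for a risk difference (Newcombe), searched over all pairs of counts with equal arms. The maximum falls at half the children in each arm, where the half-width is √2 × the Wilson half-width for one arm:

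- 20/40 versus 20/40: Wilson limits 0.352 to 0.648, half-width 0.148; √2 × 0.148 = 0.209, about 21 points
- 25/50 versus 25/50: Wilson limits 0.366 to 0.634, half-width 0.1336; √2 × 0.1336 = 0.189, about 19 points

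Siblings are treated as independent. Under the current rule there is no numerator in either arm, so adverse event records give no rate or interval for these events.

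**The case against.** The strongest reply is that this is a stated design choice. The vaccine is licensed, given to both arms to the manufacturer's specification, and no objective in section 1 concerns safety. The harms discussed in section 2.2 are vitamin toxicities, which are recorded at all grades unless labelled vaccine-associated. Many ambiguous events could be rated Possible and kept. The safeguards in the table catch some of the rest, and serious or surprising events are the likeliest to be caught. Added events would be unsolicited and partly recalled over 28-day gaps, so a low upper limit on reported events could reassure falsely.

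Most of this stands and sets the weight. It does not dispose of the point. The licensed vaccine's known profile does not cover the randomised combination, and the rule has no stated exception for serious or ambiguous events.

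Four stronger readings are tempting and are not supported:

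- **That a vitamin effect should be expected to show up as vaccine reactions.** No section says so; it is an assumption.
- **That the rule removes data from a planned comparison.** Section 11.4 plans no adverse event analysis. That gap is separate and also affects the events that are recorded.
- **That serious vaccine-attributed events would escape all oversight.** Section 9.1 ties IRB reporting to research participation, not to the gummy alone, and section 10.2 provides for review of serious event reports.
- **That the filter favours one arm.** Attribution is blinded; dilution is the more likely effect.

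**Conclusion.** The point holds as a cheap improvement, not as an error that threatens the trial's conclusions. As written, events labelled vaccine reactions cannot be compared systematically by arm, some gummy-related or joint events may be lost with them, and the exclusion sits awkwardly with section 7.1. The antibody endpoints are unaffected.

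The size is modest. Even full recording would support description only, at the precision shown above, and those limits would describe reported events rather than true reaction rates. The conclusion rests on the text and on the gummy and vaccine being given at the same visits. It needs no assumed event rate; the dilution figures are illustration, and the 50-per-arm figures assume that all 100 enrolled children are dosed.

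**What to change.** Delete the exclusion sentences in sections 6.0 and 9.2. Record all adverse events over the existing window, enrollment through last visit, regardless of presumed cause. Carry relationship to gummy and relationship to vaccine as two separate blinded fields. In section 6.5, ask caregivers to inform the study as well as the PCP. In section 11.4, add a descriptive by-arm table among all dosed children (any event, and by grade) with risk differences and 95% intervals and no hypothesis test. Label it as reported events.

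If the exclusion is kept, the minimum is one sentence in section 9.2 stating that serious events, and events possibly due to either product, are always recorded.

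The cost is more entries on the existing form, one attribution field, a revised caregiver instruction and one table; no new visit or sample. The downside is more low-grade entries to assess in about 80 to 100 children, and a table that will not be a complete count of reactions.
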